Objective 1: To evaluate the comparative effectiveness of patient-centered messages to enhance clinical trial participation, through a culturally tailored website, accessed using iPads, versus NYU's standard clinical trial participation website.

Hypothesis 1: Participants exposed to tailored messages about clinical trial literacy will exhibit greater likelihood in participating in clinical trials than those exposed to NYU's standard website.

Objective 2: To determine whether psychosocial factors (awareness of clinical trial, intrinsic motivation, health literacy, and self-efficacy) and medical factors (risk behavior, history of preventive behavior, and clinical diagnoses) mediate greater likelihood of participating in clinical trials among individuals exposed to the intervention.

[figure not shown]
Hypothesis 2: Greater likelihood of participating in clinical trials will be mediated by greater health literacy and self-efficacy independent of other individual-level factors (medical, knowledge, attitude/beliefs, and intrinsic motivation) and contextual-level factors (social support and socio-economic position).

Study Design

Objective 1: To evaluate the comparative effectiveness of a culturally and linguistically tailored clinical trial literacy website in increasing likelihood of participating in clinical trials. To achieve this objective, we will use a randomized group design, assessing the following patient-centered outcomes: willingness to enroll in clinical trials and behavioral intent as well as likelihood of referring others to enroll in such trials) before and after exposure to a culturally-tailored clinical trial literacy website. Health literacy will be measured both before and post exposure to tailored messages.

Participants will be randomized into two groups. The intervention group (n=50) will have access to culturally tailored website. Participants in the control group (n=50) will have access to NYU 's standard trial participation website.

Study Flowchart

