In addition, we will also obtain participants from research match, an online tool used to bridge individuals who are seeking out research studies and researchers who are looking for participants. Participants will be contacted via phone to ascertain their level of interest and eligibility. If participants express interest, they will be invited to come to our project office. Then, a member of the research team will provide detailed information about the study protocol, and read the consent form. Participants will have time to answer questions. No study procedures are conducted without written consent.

Second, in addition to this existing pool of potential participants, others will be recruited who meet the study criteria through community steering committee members, health fairs, and community events. At this time, recruitment will be conducted on site at the requisite health fair or community event. Study fliers will be available for participants who are interested in the study. Participants will have the opportunity to ask the study personnel questions about the study. Those who express interest will be scheduled for an enrollment session to join the study at the Center for Healthful Behavior Change to begin the enrollment process.

For the eligible participants contacted via telephone, the trained research assistant placing these calls will 1) provide detailed information about the study protocol 2) discuss requirements and expectations of participants, and 3) ascertain interest in moving forward with the study. Participants who are interested will be scheduled into an enrollment session. Participants will have time over the phone with the trained research assistant, and also during their assigned enrollment session, to answer questions of the investigative team.

Study Intervention

Participants randomized to the intervention arm will have free access to a password protected interactive culturally and linguistically tailored website via a tablet device. No private identifiable data about you will be collected. Participants will receive a brief 10-

minute tutorial by a trained research assistant on login procedures and use of the website.

Control Condition

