Data acquisition for objective 1: We will use a randomized group design, assessing patient-centered outcomes (health literacy, willingness to participate in a clinical trial, willingness to refer others), contrasting participants who were exposed to health messages via NYU's standard clinical trial website (<http://www.med.nyu.edu/oct/home>) [control arm] and those exposed to the newly created culturally and linguistically tailored website [intervention arm]. They will all complete measures at baseline assessing demographics, general health status (Medical Outcomes Study Short Form), baseline health literacy measures (National Assessment of Adult Literacy), and willingness to participate in a clinical trial ("On a scale from 1 to 5, with 1 being 'not at all willing' and 5 being 'very willing', how willing would you be to participate in a clinical trial in the future?" Response anchors will be; not at all willing, somewhat unwilling, neutral, somewhat willing, and very willing).

At the 1-month debriefing, we will reassess participants' willingness to participate in a clinical trial, and ask whether or not they opted to register with ResearchMatch; an online volunteer clinical research registry. These data will help establish a model for future translational and dissemination research. At the end of the 2-year project, we expect to have developed a culturally-tailored clinical trial literacy website that could be widely accessed. There are over 31,000 racial/ethnic minority barbershops, beauty salons, and faith-based organizations across the United States that could use this non-traditional model promoting participation in clinical trials. The long-term goal is to use this infrastructure for dissemination of evidence-based clinical trial health literacy and participation at the community level.

Schedule of Events

The primary aim of this study is to compare the tailored materials to control information only materials that are not tailored to the population being studied. However, before the Intervention/Control study, all messages and online resources will be assessed using cognitive heuristic testing to ensure the website is user friendly and culturally and linguistically tailored to the population. Heuristic testing to ensure cultural and linguistic appropriateness of the resource will be conducted, followed by the Intervention/Control study.

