Medical Outcomes Study Short Form 36	X		
Internet Self-efficacy Scale	X	X	X
Clinical Trials Literacy	X	X	X

Message Effectiveness Scale		X	X
Clinical Vignette			X

IV. DATA ANALYSIS AND DATA MONITORING

Throughout the study, [name] will oversee data entry and verification, ensure adherence to coding, clean and edit protocols. Data will be maintained on a password-protected PC with backup copies kept on external disks in a secured location.

Participant-identifying information will be kept in a locked file cabinet with only numerical identifiers in computer files.

Hypothesis 1: Participants exposed to tailored messages about clinical trial literacy will exhibit greater likelihood in participating in clinical trials than those exposed to NYU's standard website. Secondly, we expect them to show greater likelihood to refer others to clinical trials as well.

Analysis: While the primary goal of the study is to develop and test effectiveness of tailored messages to overcome identified barriers to participating in clinical trials, the secondary goal is to examine factors likely to facilitate adoption of such messages. All participants in the intervention arm will have been exposed to all tailored web-based messages. To compare participants who exhibited improvement in health literacy and those who did not 2-months post-enrollment, t-tests and chi-squared tests will be used. Baseline subjective factors will be entered in a logistic regression model in order to determine which factors are associated with higher likelihood of (a) registering to participate in clinical trials, contrasting individuals in the two study arms and (b) referring others to participate as well. Multivariate analysis of covariance will be used to assess effects of messages on the secondary outcome: health literacy scores; effects of sociodemographic confounders will be adjusted.

Hypothesis 2: Greater likelihood of participating in clinical trials will be mediated by greater health literacy and/or self-efficacy independent of other individual-level factors (medical, knowledge, attitude/beliefs, and intrinsic motivation) and contextual-level factors (social support and socio-economic position).

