Analysis: We will examine the path toward greater participation in clinical trials using Structural Equation Modeling (SEM). SEM will determine influences of mediating/moderating factors on the role of tailored messages in improving participation rates in existing clinical trials. Specifically, we will use moderated path analysis from Baron and Kenny's model. We chose these factors based on research showing acceptable effect size in predicting likelihood of increased participation. Alternatively, we will employ probabilistic modeling methods (e.g., Bayesian Belief Network) to investigate interactions (omni-directionality) among predictors and different pathways to the desired study outcomes, determining which factors best differentiate cases and controls. Thus, we will ascertain patient characteristics most likely to show improvement in rates of participation.

V. STATISTICAL PLAN

Power Calculations: Primary Objective: Assuming a medium effect size ($d = 0.32$), as derived from Cohen, and a sample size of 100, the study will be adequately powered (> 80%) to detect significant differences between participants likely to show improvement in health literacy scores and those who are not using Fisher's Exact tests (critical $X^2 = 6.58$). This will also permit detection of a significant increase in the number of participants in the intervention arm opting to register for clinical trials. In a previous pilot study, we found that 45% of minority patients in the community adopted recommendations for medical treatments after exposure to tailored health messages, which compares to 25% who did without such exposure. Assuming a 20% increase in the likelihood of adopting health messages and a sample size of 100, the proposed study will have adequate power for a preliminary test of the hypothesis that exposure to health messages will foster greater uptake of tailored health messages and improvement in clinical trial health literacy level. Achieving the goal of a 20% increase would have an important public health impact regarding adoption of messages about clinical trials. A two-tailed test, with 80% power and $\alpha = 0.05$ comparing 25% to 45% requires 50 participants per arm. The study is powered to assess differences in participation rates between the two arms as well as the mediating effect of individual and contextual factors between tailored clinical trial messages and participation rates, considering a 23% attrition rate.

VI. DATA HANDLING

Confidentiality

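### ResearchMatch both supplies participants and is the only registration measure described, and nothing listed separates people already registered from new registrants

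*Combined protocol and SAP*

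**What the plan says.** Section II.1 (Recruitment) lists several sources for the 100 places: a pool of about 400 people from completed studies, community contacts and events, and ResearchMatch. On the last it says that "we will also obtain participants from research match, an online tool used to bridge individuals who are seeking out research studies". No number or share is given for any source.

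Section III (Data acquisition for objective 1) says that at 1 month staff will reassess willingness and "ask whether or not they opted to register with ResearchMatch; an online volunteer clinical research registry". This is the only registration measure described anywhere. It has no reference period.

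The baseline battery in the same section begins "They will all complete measures at baseline assessing demographics, general health status" and continues with health literacy and willingness. Registry status is not listed there, and Table 1 has no registration row at any visit. The inclusion and exclusion criteria (II.7 and II.8) do not mention registry membership.

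Section IV (Hypothesis 1, Analysis) plans a logistic regression for "registering to participate in clinical trials, contrasting individuals in the two study arms", with no rule for people already registered. Section V says that the sample permits detection of a "significant increase in the number of participants in the intervention arm opting to register for clinical trials". Neither section names ResearchMatch. The outcomes listed in the Study Design text for Objective 1 are "willingness to enroll in clinical trials and behavioral intent as well as likelihood of referring others to enroll in such trials", and registration is not among them.

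**The concern.** A participant found through ResearchMatch is already using it when first contacted. Others, from the earlier-study pool or from community events, may also be registered. Neither website can change the status of these people, yet the 1-month question is put to them as to everyone else.

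Two things are at stake for this one behavioural measure. First, its meaning: if prior registrants answer yes, the reported rate in each arm mixes uptake during the study with membership before it. If some answer yes and others no, the item has no single definition. Second, its sensitivity: people who cannot respond to the intervention dilute the contrast between arms. Without a record made before exposure, prior status could later be recovered only from recall or from recruitment records that the plan does not say to keep.

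**Working it through.** **Inputs from the documents.** Section V gives 25% vs 45%, two-sided alpha 0.05, 80% power and 50 per arm. The two rates come from an earlier pilot on adopting treatment recommendations. They are not registration rates and serve here only as stand-ins. Section V also states that the study is powered "considering a 23% attrition rate".

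**Assumed input.** f, the share already registered, taken as equal in both arms. The documents give no value. I use 2% to 10%, because two other sources also fill the 100 places. Nothing in the documents caps f at 10%.

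**The plan's own figure first.** The usual two-proportion formula, with pooled variance under the null and mean rate 0.35, is

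n = [1.960 × √(2 × 0.35 × 0.65) + 0.842 × √(0.25 × 0.75 + 0.45 × 0.55)]² / 0.20² = 88.1, so 89 per arm.

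The stated 50 per arm does not reproduce. At 50 per arm power is 56% by this approximation and 48% by an exact two-sided Fisher test. That shortfall exists at f = 0 and is a separate matter.

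**Effect of prior registrants.** Let p be the rate of new registration among those not yet registered.

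- Counted as yes: observed rate f + (1 − f)p, with n per arm.
- Counted as no: observed rate (1 − f)p, with n per arm.
- Excluded: rate p, with n(1 − f) per arm.

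Under either of the first two codings the arm difference is (1 − f)(p₂ − p₁). At f = 2% that is 0.98 × 20 = 19.6 points, and at f = 10% it is 0.90 × 20 = 18 points.

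At f = 10%:

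- Yes coding: 0.10 + 0.90 × 0.25 = 32.5% against 0.10 + 0.90 × 0.45 = 50.5%.
- No coding: 0.90 × 0.25 = 22.5% against 0.90 × 0.45 = 40.5%.
- Excluded: 25% against 45%, with 50 × 0.90 = 45 per arm.

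Power is Φ{[difference − 1.960 × SE₀] / SE₁}, with SE₀ pooled and SE₁ unpooled. For yes coding at f = 10%, SE₀ = 0.0985 and SE₁ = 0.0969, so (0.18 − 0.1931)/0.0969 = −0.136 and power is 44.6%.

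| f (assumed) | 50 per arm: yes / no / excluded | 38.5 per arm: yes / no / excluded |
|---|---|---|
| 0 | 56% | 45% |
| 2% | 53 / 54 / 55% | 43 / 44 / 44% |
| 5% | 50 / 52 / 53% | 40 / 42 / 43% |
| 10% | 45 / 49 / 51% | 36 / 40 / 41% |

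The last column assumes that all of the 23% attrition falls before 1 month: 50 × 0.77 = 38.5.

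**Reading the table.** At f = 10% and 50 per arm, exclusion gains 51.2 − 44.6 = 6.6 points over yes coding, but only 51.2 − 49.1 = 2.1 points over no coding. After attrition the gains are 41.3 − 35.8 = 5.5 and 41.3 − 39.6 = 1.7 points. Most of the benefit comes from ruling out yes coding.

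**The case against.** The strongest reply is that opting to register, asked after a month of website access, naturally means a new act, so prior registrants would answer no. That is a fair reading. It would leave only about 0–2 points of power to gain from excluding them, and a time anchor in the 1-month question would secure most of the benefit without a baseline item. But the text does not settle the meaning, and someone recruited through ResearchMatch could honestly answer either way.

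Other parts of the reply also stand. The link from this question to the registration outcome in sections IV and V is inferred. The survey forms are not in the documents, and the demographic and clinical row of Table 1 is not itemised, so a status question may exist; even then, no analysis rule uses it. The size is unanchored, because f is unknown and the rates are borrowed. The plan names Fisher's exact test and logistic regression, so the normal-approximation figures are only illustrative.

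Cueing is a real cost. If naming ResearchMatch at baseline raised registration by an assumed 5 points in both arms, power with 45 per arm would be 49.0%, which cancels the gain over no coding.

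A reader might infer that the overlap favours one arm. The documents do not support that: allocation is randomised, so prior registrants are balanced in expectation, with chance imbalance remaining. A reader might also infer that the trial's main comparison is compromised. Willingness, referral and literacy do not depend on registry status being new.

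**Conclusion.** The point holds as an undefined outcome with a modest cost. One service is both a recruitment source and the only registration measure described, and nothing listed separates prior from new registrants. If prior registrants count as yes, both arms' rates are inflated. Whether they count as yes or as no, the expected difference falls to (1 − f) of its value.

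With the stand-in rates, 50 per arm and f at the top of the assumed range, power falls from 56% to 45% under yes coding or 49% under no coding; exclusion gives 51%. These figures rest on an assumed f, borrowed rates and a normal approximation. It would be wrong to attribute the gap from the claimed 80% power to this overlap, since that gap is present with no prior registrants at all. This is a cheap improvement worth considering, not a flaw that invalidates the trial.

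**What to change.** - Define the outcome as new ResearchMatch registration since enrolment, and word the 1-month question to match (for example, since you enrolled). This step brings most of the gain.
- Record each participant's recruitment source.
- Ask everyone the same question on current registration in the baseline survey, ideally within a neutral list of registries to limit cueing. Section II.1 says that "No study procedures are conducted without written consent", and in section III the arm-specific sessions (Baseline II) come before the consent forms (Baseline III). The baseline survey (Baseline IV) follows consent and precedes the tablet, so the item fits there without reordering.
- Analyse this outcome among those not registered at baseline, report f by arm, and keep prior registrants in all other analyses.
- State in section IV whether this item is the registration outcome that is modelled there and cited in section V.

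The cost is one baseline item, one recorded field, one reworded question and a sentence or two in the analysis plan. The downsides are a smaller denominator (at f = 10%, 45 per arm before attrition and 38.5 × 0.90 ≈ 35 after) and possible cueing in both arms, of unknown size. If cueing is judged the greater risk, the anchored question and the recorded recruitment source alone would still remove most of the ambiguity, though they would miss prior registrants who came from other sources. None of this addresses the separate power shortfall.

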Participants randomized to the control condition will have free access to the NYU standard clinical trials website. Currently, there is no specific comparative effectiveness data evidencing superiority of any website or other format for increasing clinical trials literacy. Furthermore, there has been previous research to suggest the overall difficulty that patients have in using generic, versus tailored clinical trial materials. This, our study will ascertain effectiveness of a tailored website compared to the standard website. Participants in the control condition will have access to the tailored website at the date of study completion (no later than 6 months' post-date of enrollment).

2. Process of Consent

We will explain to participants that the purpose of the study is to understand barriers pertaining to why blacks do not participate in clinical trials, assess their willingness to enroll in clinical trials, and ascertain whether or not they will refer others to participate in such trials. We will obtain participants consent to audio-record the debriefing session. The screening team will comprise ethnically concordant investigator: [name]. All participants will be reminded that their responses are confidential and that they may refuse to participate in the project or withdraw at any time without explanation, and further, that such action will in no way affect their future interactions with their health care provider, or with New York University Medical Center. To ensure confidentiality, data will be associated with an individual participant only by an assigned identification number, the code for which will be kept in a locked drawer that only the study investigators will have access to.

3. Number of subjects.

The proposed study expects to recruit a total of 100 participants from all recruitment strategies over a period of 9 months.

4. Gender of Subjects.

The study will include black men and women

5. Age of Subjects.

The sample frame will include black men and women 18 years old and older.

6. Racial and Ethnic Origin.

Our emphasis on blacks is justified by the low participation in clinical trials in this group.

7. Inclusion Criteria.

Self-reported race/ethnicity as African American, African, Caribbean American or black men and women; ages ≥ 18 years; accessible by telephone; no plans to move away from the region within the year following enrollment; consent to participate.

8. Exclusion Criteria.

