Progressive medical illness in which disability or death is expected within one year; impaired cognitive or functional ability, which would preclude meaningful participation in the study; stated intention to move within the same year of enrollment.

9. Vulnerable Subjects.

This study does not involve vulnerable subjects

10. Subject/Representative Comprehension.

Participants will be asked to repeat back to the research assistant the salient points of the consent form to make sure that they understand the study they are agreeing to participate in. Children and/or decisionally impaired adults will not be subjects in this study.

11. Debriefing Procedures.

Information will not be purposely withheld from the subject. Participants will be asked to sign the audio-consent form. An audio-recording will be obtained for an accurate summary of the debriefing process. At the three-month follow-up visit, participants will be asked to provide overall feedback and experience about the study to encapture content that may not otherwise be received through the survey measures. The audio-recording will be held in perpetuity to evaluate after the study is closed. Participants will be given the opportunity to ask questions, and provide comments on the study importance.

12. Consent Forms.

We will use consent forms approved by the IRB. All participants will be reminded that their responses are confidential and that they may refuse to participate in the project or withdraw at any time without explanation, and further, that such action will in no way affect their future interactions with their health care provider, or with New York University Medical Center. To ensure confidentiality, data will be associated with an individual participant only by an assigned identification number, the code for which will be kept in a locked drawer.

13. Costs to the Subject.

There will be no costs to study subjects.

14. Payment for Participation.

Participants in Phase I Heuristic Testing will receive \$50 for providing baseline data. Participants in Phase II (Intervention/Control) will receive \$25 at baseline, \$50 at the 1 month follow up period and \$25 at 3 months.

III. STUDY DESIGN/METHODS

Using data from previous RCTs (R25H116378, R01MD004113, and R01MD007716, we will use previously gathered data on barriers and facilitators to clinical trial participation

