Our collaborator from SUNY Downstate, [name], will conduct heuristic evaluation and cognitive walkthroughs of all web materials, and then perform standard formative usability testing onsite with 10 representative participants to ensure the site is well-suited to the needs of the intended community. These participants will be recruited from the existing pool of participants from previous RCT's mentioned above..

Participants will be contacted, and recruited for this portion of the study via telephone. Participants will be scheduled into time slots of approximately 40 minutes in duration. Participants will come to CHBC at their assigned timeslot, read and sign the consent form, and then begin the heuristic testing. She will ascertain whether health materials are acceptable and whether they capture daily experiences of potential patients whose lives vignettes intend to portray. She will recommend necessary changes based on log-file analysis that captures computer activity while the participant uses the website. In addition, [name] will ask participants several debriefing questions, such as their experience with the Internet, their willingness to use the resource in the future, and their overall user experience. This will ensure that messages are credible and understandable to the partner community.

Materials will also be presented to stakeholders in our Community Advisory Board for final approval. Once approved, materials will be available for use in the Intervention/Control Study.

Intervention/Control Study

Participants in the Intervention/Control study will be asked to come to the Center for Healthful Behavior Change for three discrete visits, including baseline, 1-month follow up, and 3-month follow up.

Baseline:

- I. Participants will be contacted from our prior IRB approved studies. Potential participants recruited through community locations and events like health fairs will also be contacted. All potential participants will be scheduled into an enrollment slot at which time they arrive at the CHBC ([name]) to fill out baseline surveys and receive study instructions.
- II. When participants arrive, they will be invited to go to either the intervention or control enrolment sessions. These groups will remain separate so as not to cross-contaminate instructions or materials.

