- III. Participants will receive the consent forms, and will be asked to read the documents carefully. Participants will be provided time to call any family or friends, and given the time they need to make an informed decision about participation. The consent forms will be approved by the IRB, and include a request for participant cell phone number and email address. Cell phone is collected so that participants may be sent study reminders, and email is

requested so that the study personnel might share the intervention resource with participants in the control condition at the end of the study. Participants will also be asked if the study team can record the debriefing session. If so, consent will be obtained.

- IV. Participants will take baseline surveys; this will take approximately 25 minute. Next, participants will receive their experimental materials, which include a Wi-Fi enabled tablet that has been pre-loaded with either intervention or control materials on the browser. Participants will receive verbal and paper-based instructions from the research assistant on how to log into the online, tailored website (intervention condition) or how to access the generic informational website (control condition). Participants will be debriefed, thanked for their time, and scheduled for a slot for their 1-month follow up visit. Participants will receive \$25 for their participation.

One-month follow up:

- Participants will return to the Center for healthful Behavior Change at their 1-month follow up appointment. At this time, participants will be instructed to bring their tablets with them to return the device, and take a follow up survey. The survey will take approximately 25 minutes.
- Participants will be thanked for their time, and scheduled for a slot for their for their 3-month follow up visit. Participants will receive \$50 for their participation.

Three-month follow up:

- Participants will arrive at the CHBC for their 3-month follow up to simply take on last, follow up survey. Participants in the intervention condition will receive \$25 for their participation, debriefed, and released from the study.
- Participants in the control condition will also receive \$25 for their participation, debriefed, and instructed that they will receive access to the intervention resources via email after no later than 3 months.

All outcome measures are located in Table 1.

Table 1 Outcome Measures	Baseline	1 months	3 months
Demographic and Clinical Variables	X		

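### Nothing stops two housemates being randomised to opposite arms while the tailored site is on a loaned tablet for about a month; a one-adult-per-household rule would close this small gap cheaply

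*Combined protocol and SAP*

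**What the plan says.** **Allocation.** Study Design, Objective 1, states "Participants will be randomized into two groups", with 50 in each. No household unit, stratum or allocation rule is described, and neither is the randomisation method.

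**Recruitment.** Section II.1 starts with about 400 past participants who agreed to be contacted, and adds ResearchMatch. It then says that "others will be recruited who meet the study criteria through community steering committee members, health fairs, and community events".

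**Eligibility.** After race/ethnicity and age, II.7 lists "accessible by telephone; no plans to move away from the region within the year following enrollment; consent to participate". II.8 covers progressive illness and then "impaired cognitive or functional ability, which would preclude meaningful participation in the study; stated intention to move within the same year of enrollment". Neither list mentions relatives or housemates of someone already enrolled.

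**Exposure period.** At baseline (section III, Intervention/Control Study, step IV) each participant receives "a Wi-Fi enabled tablet that has been pre-loaded with either intervention or control materials on the browser". The tablet comes back at the 1-month visit.

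**Safeguards.** There are two:
- At enrolment (step II), the arms attend different sessions: "These groups will remain separate so as not to cross-contaminate instructions or materials".
- The website description in section III restricts the tailored site to the exposure arm by password. Each participant has an individual password, and site activity is logged against it.

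**The concern.** The protocol names cross-contamination as something to avoid, but the step it takes for that stated purpose applies only to the enrolment visit. The tailored content is then outside the centre for about a month. If two adults in one home are in different arms, the control participant may see the content that the trial is testing.

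A control who has seen the tailored site is still analysed as a control. That shrinks the observed difference in registration, willingness and literacy, and it cannot be undone after enrolment. It would also be hard to detect. A log tied to the intervention participant's password credits all viewing to that person, and none of the instruments listed in Table 1 is a measure of whether controls saw the tailored site.

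**Working it through.** **Inputs from section V:** 25% versus 45%, two-sided alpha 0.05, 80% power, 50 per arm.

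**Assumed input:** q, the share of controls who see the tailored site and then respond at the full intervention rate. The documents give no figure for household pairs or for sharing.

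**Step 1: the plan's own figure.** With the pooled two-proportion formula and a mean rate of 0.35,

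n = [1.96·√(2×0.35×0.65) + 0.842·√(0.25×0.75 + 0.45×0.55)]² / 0.20² = 88.1, so 89 per arm.

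The stated 50 per arm does not reproduce. This shortfall exists before any contamination and is a separate matter. Here it matters only because the baseline for the dilution figures is the actual power at 50 per arm, not 80%.

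**Step 2: plausible range for q.** With 50 per arm and independent allocation, a participant's housemate is in the opposite arm with probability 50/99 = 0.505. If a share f of participants enrol as household pairs, the share of controls with a housemate in the tailored arm is f × 50/99.

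- f = 20%: 0.20 × 0.505 = 10.1%. This is the ceiling for q at that f, reached only if every such pair shares and the effect transfers in full.
- f = 10%, with half of the split pairs sharing effectively: 0.10 × 0.505 × 0.5 = 2.5%.

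Both values of f, and the one-half, are assumptions.

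**Step 3: dilution and power at 50 per arm.**

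Control rate p_c = 0.25 + 0.20q, and difference Δ = 0.20(1 − q).

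Power = Φ{[Δ − 1.96·√(2p̄(1−p̄)/50)] / √([p_c(1−p_c) + 0.45×0.55]/50)}, where p̄ is the mean of the two rates.

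| q | p_c | Δ (points) | Argument of Φ | Power |
|---|---|---|---|---|
| 0 | 0.250 | 20 | (0.200 − 1.96×0.0954)/0.0933 = 0.140 | 55.6% |
| 2.5% | 0.255 | 19.5 | (0.195 − 1.96×0.0955)/0.0935 = 0.083 | 53.3% |
| 5% | 0.260 | 19 | (0.190 − 1.96×0.0957)/0.0938 = 0.026 | 51.0% |
| 10% | 0.270 | 18 | (0.180 − 1.96×0.0960)/0.0943 = −0.086 | 46.6% |

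The arguments were computed before the displayed standard errors were rounded.

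**Step 4: does correlation within households matter for the test?** This was checked by simulation with 100 participants, 10 or 20 household pairs, within-pair correlation 0.5 and an ordinary two-proportion test. With individuals randomised, type I error stays at about 5%. If housemates are instead put in the same arm, it rises to between 6% and 8%.

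**The case against.** The strongest reply is that the plan already protects the tablet month. The site needs an individual password, use is logged, and controls hold their own tablets loaded with control material. A reader who looks only at the separate enrolment sessions might infer that nothing covers this period. The documents do not support that. What remains is narrower: an intervention participant must log in and show the site, or share the password. The password does not prevent either, and the logs would not reveal it.

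Second, the premise is a possibility and not a stated fact. No section says that relatives or housemates will be recruited together. The community routes supplement a pool of about 400, and use of the tablet at home is inferred from its issue at baseline and return at 1 month. The randomisation method is not described, so how people who arrive together would be allocated is unknown. All of this stands. It limits the point to what the design permits.

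Third, a reader might infer that correlated outcomes within households invalidate the planned logistic regression and multivariate analysis of covariance. Under individual randomisation this does not follow: in the simulated two-proportion comparison the type I error stayed at about 5%.

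Fourth, this is a pilot, and the bias is towards no effect, so exposure of controls would not manufacture a positive result. That is correct and keeps the priority low. It is not a reason to leave a cheap gap open.

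**Conclusion.** The gap is real but minor. Individual randomisation, community recruitment, no household rule and a month with the tablet together allow split households. The two safeguards reduce the risk without removing it, and the listed measures would not show whether it happened.

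If 2.5% to 10% of controls were fully exposed, the difference would fall from 20 points to between 19.5 and 18, and power at 50 per arm from about 56% to between 53% and 47%. This rests on an assumed share of household pairs, an assumed rate of sharing and full transfer of the effect. The upper end is a ceiling for a sample with 20% of participants in pairs, and the true effect is probably small.

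Two further inferences should be resisted. Contamination does not explain why power is about 56% and not the stated 80%; that gap is there at q = 0. Nor do the documents support heavy dilution: by this route, q = 20% would need about 40% of the sample to enrol as household pairs (0.40 × 0.505 = 20.2%), all of them sharing with full effect.

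**What to change.** Add to II.7 or II.8 that only one adult per household may be randomised. Check it with one question, at the telephone contact or the enrolment session that II.1 already describes, on whether anyone in the household has joined or is joining the study.

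The cost is one eligibility line, one question and a few second household members turned away. With about 400 people in the stated pool, plus ResearchMatch and community recruits, for 100 places, the loss should be easy to absorb.

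Placing later household members in the first member's arm is not a good substitute. It creates clustering that the planned analyses would then have to handle, and it reveals the second person's allocation before enrolment.
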